4.2 General presentation of descriptive summaries and listings

The following summary statistics will be presented unless otherwise stated specifically. Qualitative/categorical data (e.g., gender, race) will be summarized by frequency counts and percentages. Percentages will be calculated using the number of patients in the relevant treatment arm or subgroup as the denominator.

Continuous data (e.g., age, body weight) will be summarized using appropriate descriptive statistics (i.e. mean, standard deviation (SD), median, minimum and maximum) by treatment arm.

Based on the nature of the data, few analyses require additional statistics such as geometric mean, geometric coefficient of variation (CV) and it will be specifically requested in respective section.

In general, listings will be presented

- with country/center/subject identifier and age/sex/race as mandatory columns unless otherwise specified
- by treatment, patient and chronological time

4.3 General definitions

Study treatment:

Study treatment will be noted as VAY736/Placebo throughout this document and CSR deliverables.

Study day:

The study day for safety/efficacy assessments (e.g. adverse event onset, laboratory abnormality occurrence, vital sign measurement, Electrocardiogram (ECG), PK sampling, FVC values, etc.,) will be calculated using the randomization date as the reference date. For assessments occurring: **on or after the randomization date**, the study day will be calculated as (date of assessment/occurrence) – (date of randomization) + 1. Then study day 1 will be the day of randomization.

before the randomization date, the study day will be calculated as (date of assessment/occurrence) – (date of randomization).

For example, if a serious adverse event starts 1 day before the randomization date, the study day displayed on the listing will be negative, i.e. -1.

Baseline:

For all evaluations, the last available pre-dose assessment before or on the date of randomization is taken as 'baseline' value or 'baseline' assessment.

Commercially Confidential Information

Unscheduled assessment:

There will be no analysis visit window defined, by consequence descriptive summary statistics by visit will not include unscheduled/repeat assessment.

For all analyses regarding abnormal assessments or analyses based on worst post-baseline value (e.g. laboratory, ECGs, vital signs), all post-baseline values will be included (scheduled, unscheduled, repeat). All unscheduled and repeat measurements will be included in listings.

Treatment analysis epoch:

Treatment epoch will be defined as any post-baseline assessment performed between the first dose of study drug date and the date of Week 49 visit if not missing or the date of last visit attended in treatment epoch (End of Study Treatment visit 199) in case of drop-out or the death date if subject died in treatment epoch.

Commercially Confidential Information

5 Statistical methods for Pharmacokinetic (PK) parameters

5.1 Variables

Commercially Confidential Information

No derivation of PK parameters is planned for this study but a modeling of the data may be performed possibly pooling these data with data coming from previous studies. This optional analysis will be described and reported separately in a modeling plan and a modeling report as appropriate.

5.2 Descriptive analyses

Commercially Confidential Information

Summary statistics will include mean (arithmetic and geometric), Standard Deviation (SD), Coefficient of Variation (CV) (arithmetic and geometric), median, minimum and maximum. At each visit, geometric means and CVs will not be reported in case of concentrations below LLOQ or zero values.

Commercially Confidential Information

Arithmetic CV is defined as: $SD*100/Arithmetic\ mean$.

Geometric CV is defined as: $100*\sqrt{exp(sdlogs**2)-1}$, where sdlogs represents the SD of log-e transformed data.

5.3 Statistical model, assumptions and hypotheses

Modeling of the data may be performed as appropriate. As the PK data from the current study may be pooled with data from previous studies, the PK analysis will be described and reported separately in a modeling plan and modeling report.

5.3.1 Model checking procedures

Not applicable.

5.3.2 Graphical presentation of results

Individual concentration-time profiles and mean profiles with SD bars will be presented.

6 Statistical methods for Pharmacodynamic (PD) parameters

6.1 Primary objective

The primary objective of the study is to assess the efficacy of VAY736 on top of current standard-of-care therapy (pirfenidone, nintedanib, or no treatment) using FVC (L) at the end of treatment epoch (48 weeks of treatment) in patients with idiopathic pulmonary fibrosis.

6.1.1 Variables

The primary endpoint is the change from baseline in FVC (L).

6.1.2 Descriptive analyses

Summary statistics of change from baseline in FVC by treatment and visit will be presented by epoch. In addition to the overall summary a summary by baseline standard-of-care medication (stratification factor: pirfenidone, nintedanib, or no treatment) will be produced.

Individual data will be listed by treatment, epoch and visit.

Commercially Confidential Information

6.1.3 Statistical model, assumptions and hypotheses

The following hypothesis will be tested for VAY736+SoC versus Placebo+SoC:

H0: There is no difference or worsening in change from baseline in FVC (L) from baseline to 48 weeks of treatment between VAY736+SoC and placebo+SoC

H1: There is an improvement in change from baseline in FVC (L) from baseline to 48 weeks of treatment between VAY736+SoC and placebo+SoC

Test will be conducted at a one-sided 10% level and 2-sided 80% CI of the estimates will be displayed. Sense of the one-sided test for each criteria is given in table of appendix 1 (section 10.1).

The primary variable, change from baseline in FVC (L) will be analyzed using a Mixed Effects Model for Repeated Measures (MMRM) in the PD analysis set and considering all assessments collected during the treatment epoch. The model will include treatment and visit as fixed effects, standard of care treatment (Nintedanib, Pirofendone, or no treatment) as factor and baseline value as a covariate, treatment-by-visit and baseline-by-visit as interaction terms. The within subject correlation will be modeled using a repeated statement in SAS Proc Mixed with unstructured covariance matrix. In case of non convergence the model, an alternative AR(1) covariance may be implemented. The posterior will be derived as a t-distribution using a PROC MIXED as detailed in section 3. The main comparison will be a contrast between treatment groups at 48 weeks of treatment. This approach assumes data is Missing At Random (MAR).

Commercially Confidential Information

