2.3 Exploratory objective(s)

Commercially Confidential Information

Commercially Confidential Information

3 **Investigational plan**

3.1 **Study design**

This is an exploratory (non-confirmatory) randomized, patient-, investigator-, sponsor- blinded, placebo controlled study of VAY736 in IPF patients. This study will investigate the safety and efficacy of 300 mg VAY736 administered s.c. every 4 weeks for 48 weeks. Approximately 58 subjects will be randomized in a 1:1 ratio on top of local standard of care (SOC), to receive VAY736 or placebo. Randomization will be stratified by SOC treatment (3 levels: nintedanib, pirfenidone, or neither). The randomization scheme will be performed separately within each stratum to ensure balance of the treatment groups with respect to the SOC treatment.

A screening epoch of 6 weeks will be used to assess eligibility. The population will consist of patients with IPF following American Thoracic Society (ATS)/European Respiratory Society (ERS)/Japanese Respiratory Society (JRS)/Latin American Thoracic Association (ALAT) diagnostic guidelines, utilizing High-Resolution Computed Tomography (HRCT) and/or surgical lung biopsy (SLB) as medically indicated. A central reader (imaging expert) will review the screening HRCT to validate an accurate diagnosis of IPF; and a central reader (pathology expert) will review any prior SLB, if an SLB was necessary for the diagnosis of IPF (i.e., SLB was obtained in the normal course of a diagnostic evaluation). Once eligibility has been assessed during the screening epoch, eligible subjects will be randomized to one of the two treatment arms.

Randomized subjects will participate in a 48 week treatment epoch,
Comercially Confidential Information

Please refer to the Assessment Schedule ([Table 8-1](#)) for a list of procedures to be performed at each visit. Efficacy assessments will be performed quarterly (Weeks 1, 13, 25, 37, and 49) during the treatment epoch. Safety assessments will be performed at monthly or quarterly intervals during the treatment epoch. HRCT will be performed at screening and again at the end of the treatment epoch.

Comercially Confidential Information

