8.5.1 Spirometry

Spirometry testing will be performed according to the ATS guidelines ([Miller et al 2005](#)) at screening to assess patients' eligibility for the study and as detailed in the Assessment schedule ([Section 8.1](#)).

The spirometry equipment will be supplied to each site for the study. The same spirometry equipment should be used for all assessments performed by a subject. A limited number of staff, as designated by the investigator, will evaluate all patients at all visits throughout the entire trial. Where possible the same technician should perform all maneuvers for an individual subject. All staff conducting the spirometry tests must have received appropriate training which must be documented. Information on the procedures can be found in the SOM.

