11.7 Sample size calculation

In total 58 subjects are going to be randomized to the study in a 1:1 randomization. Assuming a treatment period of 48 weeks with 2 arms, VAY736+Standard-of-Care (SoC) vs. Placebo+SoC, and standard deviation of 250 ml for FVC (ml); a total sample size of 58 patients with 48 weeks data will give at least 80% power to detect a treatment improvement in change from baseline in FVC (ml) between VAY736+SoC and Placebo+SoC of 160ml in patients with Idiopathic Pulmonary Fibrosis (IPF).

The sample size calculation is based on the primary efficacy endpoint of change from baseline in FVC (ml) at week 48. The criteria for this calculation aimed for a 90% level of proof that difference in change in FVC from baseline to week 48 between VAY736+SoC and placebo+SoC > 0 and the mean treatment+SoC effect is at least 110 ml better than placebo+SoC effect. The former targets proof that the treatment+SoC produces a statistically significant improvement in change from baseline in FVC, while the latter targets proof of clinical relevance.

Commercially Confidential Information

The overall type I error at the end of study will be approximately 12% under this sample size.

If more than 20% of the randomized patients have not completed the 48 weeks of treatment, per protocol, then patients may be replaced.

R software version 3.0.3 ([Fisch et 2015](#)) was used.

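### FVC and DLCO are measured twice before dosing but the model adjusts for one value only; adding the screening value is a cheap and probably modest gain in precision

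*SAP*

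**What the plan says.** Protocol 8.5.1 has spirometry done "at screening to assess patients" for eligibility. Protocol 3.1 then states: "Efficacy assessments will be performed quarterly (Weeks 1, 13, 25, 37, and 49) during the treatment epoch". Table 8-1 marks spirometry and DLCO at Screening (Days -42 to -1) and at Visit 101 (Day 1), with a footnote placing the Day 1 tests before dosing. Each patient is therefore due two pre-dose readings of both measures.

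SAP 4.3 keeps one of them: "the last available pre-dose assessment before or on the date of randomization is taken as" the baseline, for all evaluations. The MMRM in SAP 6.1.3 has "baseline value as a covariate, treatment-by-visit and baseline-by-visit as interaction terms", and Protocol 11.4.2 specifies the same model. The imputation steps and the ANCOVA in SAP Appendix 2 likewise carry a single BASE variable. No visible text averages the two readings or uses the other one. SAP 6.2.3.2 applies the same MMRM to DLCO and to the exercise and gas-exchange endpoints.

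**The concern.** Test noise in the Day 1 reading enters every change from baseline. When patients differ widely in FVC level, adjusting for that one noisy reading removes almost none of this noise. A second pre-dose reading of the same quantity can remove up to about half of it.

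The screening reading is already collected and precedes randomisation, so treatment cannot affect it. In a 58-patient trial, any residual variance it could explain widens the interval for the primary contrast unnecessarily. DLCO has the same structure but is a secondary endpoint.

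**Working it through.** **1. The plan's own figure.** Protocol 11.7 says "a total sample size of 58 patients with 48 weeks data will give at least 80% power" for a difference "between VAY736+SoC and Placebo+SoC of 160ml", with an SD of 250 ml. SAP 6.1.3 sets a one-sided 10% level.

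- Per arm: 2 × (1.2816 + 0.8416)² × (250/160)² = 22.01, so 23. Dividing by 0.8 gives 28.75, so 29 per arm and 58 in total.
- With 29 per arm the SE is 250 × √(2/29) = 65.65 ml. Power is Φ(160/65.65 − 1.2816) = 87.6% (87.2% with the t distribution). With 23 per arm it is 81.3% (80.7%).

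The stated power holds at both sizes.

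**2. Inputs not in the documents.** No test-retest SD and no correlation between visits is given. I assume noise SD *s* per test from 50 to 150 ml and between-patient SD *t* = 700 ml. The SD of change is held at 250 ml, so the variance of true change is v = 62,500 − 2s².

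**3. Residual variance of the Week 48 change.** With complete data the Week 48 MMRM contrast is essentially that of an ANCOVA. If true FVC does not move between screening and Day 1:

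- Day 1 value only: V₁ = v + s² + t²s²/(t² + s²)
- Both values: V₂ = v + s² + t²(s²/2)/(t² + s²/2)

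Example at s = 100: v = 42,500. V₁ = 52,500 + 9,800 = 62,300 and V₂ = 52,500 + 4,949.5 = 57,449.5, a cut of 7.8%.

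**4. Degrees-of-freedom cost.** The single-baseline ANCOVA has five parameters (intercept, treatment, two for standard of care, baseline). One more covariate inflates variance by about (58 − 5 − 2)/(58 − 5 − 3) = 51/50 = 1.02. With 46 patients the factor is 39/38 = 1.026. The net cut is 1 − 1.02 × V₂/V₁, and likewise with 1.026.

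| Noise s (ml) | V₁ | V₂ | Gross cut | Net, N = 58 | Net, N = 46 |
|---|---|---|---|---|---|
| 50 | 62,487 | 61,247 | 2.0% | 0.0% | −0.6% |
| 80 | 62,418 | 59,279 | 5.0% | 3.1% | 2.5% |
| 100 | 62,300 | 57,450 | 7.8% | 5.9% | 5.4% |
| 120 | 62,089 | 55,196 | 11.1% | 9.3% | 8.8% |
| 150 | 61,512 | 50,998 | 17.1% | 15.4% | 14.9% |

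**5. Power.** These are ANCOVA simulations with 8,000 trials per setting, the standard-of-care factor included and the degrees-of-freedom penalty applied. Small differences in the starting values are simulation error.

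| Noise s (ml) | 29 per arm | 23 per arm |
|---|---|---|
| 80 | 86.3 → 87.7% | 79.9 → 81.0% |
| 100 | 87.3 → 88.8% | 80.2 → 81.7% |
| 120 | 86.6 → 89.1% | 80.4 → 83.0% |
| 150 | 87.1 → 90.6% | 80.2 → 85.0% |

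At 50 ml the simulated net variance change is close to zero: a cut of 0.5% with 29 per arm and a loss of 0.9% with 23.

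**6. True change between screening and Day 1.** The screening reading may be up to six weeks old. Take a six-week gap, so k = 6/48 = 0.125, and write c = t²s²/(t² + s²).

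- Random-walk change, with variance kv over the gap: gross cut 3.3/6.1/9.6/16.2% at s = 80/100/120/150.
- Steady patient-specific decline: the gross cut is (c − kv)²/[(s² + k²v + c)V₁], which gives 0.0/1.6/5.3/13.7%. At s = 100, (9,800 − 5,312.5)²/(20,464 × 62,300) = 1.6%. With a three-week gap the cuts are 1.3/4.1/8.0/15.4%.

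Across 80 to 150 ml, true change therefore lowers the gain, to zero in one case. The steady-decline case is not monotone: at 50 ml the same formula gives (2,487 − 7,187.5)²/(5,886 × 62,487) = 6.0%, because the pair of readings then carries information on slope.

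**The case against.** The strongest reply is that nothing here is wrong. The last pre-dose value is a coherent, pre-specified and widely used baseline. The trial is explicitly exploratory, and the stated power is met without the change. Two readings up to six weeks apart in a progressive disease are not replicates, and with low noise the added covariate buys nothing. All of this stands, and it makes the point an optional gain rather than a defect.

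A reader might infer that the plan gives up 5 to 17% of its variance for nothing. The documents do not support that. The lower figure comes from starting the assumed noise at 80 ml, whereas 50 ml gives 2.0% gross and about zero net. The upper figure is gross of the degrees-of-freedom cost. True change over the screening gap can reduce the gain further.

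Two practical objections also stand. Adding the term to the final ANCOVA alone would leave the imputation models without an analysis covariate. Adding it to SAP 6.1.3 alone would break the 6-minute-walk endpoints, which share the model but have no screening test.

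Finally, confidential text follows both the baseline definition and the primary model, and SAP section 3 is redacted. The conclusion rests on the visible text. If randomisation preceded the Day 1 test date, SAP 4.3 would select the screening value instead, but still only one value would be used.

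**Conclusion.** The point holds as a low-cost efficiency improvement. One of two scheduled pre-dose FVC readings is left out of the primary model, and including it cannot bias the comparison. Under the assumptions in the working (noise 50 to 150 ml, SD of change 250 ml, between-patient SD 700 ml, stable FVC before dosing), residual variance falls by about 2 to 17% gross and roughly 0 to 15% net. Power at 29 per arm rises from about 87% by 0 to 4 points.

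Confidence is high in the direction and only moderate in the size, because the noise SD is assumed. The worst case with stable FVC is a loss of about 1% of variance at 23 per arm. No size can be given for DLCO, since the documents contain no DLCO variance.

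**What to change.** Before unblinding:

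- Keep the endpoint as change from the Day 1 baseline.
- Add screening FVC and screening-FVC-by-visit to the MMRM in SAP 6.1.3, and align Protocol 11.4.2.
- Add screening FVC to the imputation models in Appendix 2 parts A and B and to the ANCOVA in part C.
- Make the same change for DLCO.
- State in SAP 6.2.3.2 that endpoints without a screening measurement keep the single-baseline model. These are 6MWD, distance-saturation product and, as it comes from the same test, the post-walk Borg score.
- Where screening and baseline are the same test in a patient, use that value for both covariates.
- If the MMRM does not converge, drop the screening-by-visit interaction first, before changing the covariance structure.

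The cost is a few degrees of freedom and one extra parameter per post-baseline visit, which is four on the quarterly schedule (Weeks 13, 25, 37 and 49). The text edits cover two SAP sections, Appendix 2 and one protocol section. No new data are needed. The blinded pooled SD of the Day 1 minus screening difference, divided by √2, would show how large the noise is; it would overstate the noise to the extent that FVC truly changed between the two tests.

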6.2.3.2 Pulmonary Physiology, Exercise capacity, Gas Exchange

CCI

The same MMRM model described for the primary endpoint will be used in these analyses using SAS Proc Mixed.

Commercially Confidential Information

An ANCOVA

model will be fitted with treatment group as main factor, standard of care therapy (stratification factor) as a cofactor and baseline as covariate.

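### The AR(1) fallback for the MMRM assumes equal variance at every visit; if spread grows towards Week 48 and the fallback is used, the one-sided 10% test runs at roughly 12–16%

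*SAP*

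**What the plan says.** SAP section 6.1.3 sets out the primary analysis of change from baseline in FVC. On covariance it says: "The within subject correlation will be modeled using a repeated statement in SAS Proc Mixed with unstructured covariance matrix". If that model does not converge: "In case of non convergence the model, an alternative AR(1) covariance may be implemented". No intermediate structure, heterogeneous version or robust standard error appears in the visible text, and the wording leaves use of the fallback to discretion.

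The inference rests on a single visit: "The main comparison will be a contrast between treatment groups at 48 weeks of treatment". The error rate is also fixed there: "Test will be conducted at a one-sided 10% level and 2-sided 80% CI of the estimates will be displayed".

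SAP section 6.2.3.2 carries the model over to pulmonary physiology, exercise capacity and gas exchange: "The same MMRM model described for the primary endpoint will be used in these analyses using SAS Proc Mixed". The fallback presumably goes with it.

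Protocol section 11.7 gives the only variability figure, a "standard deviation of 250 ml for FVC (ml"). Neither document gives an SD or a correlation by visit.

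**The concern.** An unstructured matrix estimates a separate variance for each visit. AR(1) estimates one variance and one correlation, so a single pooled variance is applied to Week 48.

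The outcome is change from baseline in a disease that Protocol section 1.1 describes as progressive. Patients who decline at different rates drift apart, so the spread of change would naturally be largest at the last visit, which is the one tested. Pooling with less variable earlier visits would then make the Week 48 standard error too small.

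The error would be in the direction of false success: a test labelled 10% would reject more often under the null, and the 80% interval would be too narrow. Section 6.1.3 also derives a posterior t-distribution from the same PROC MIXED fit, so that would be too narrow as well. What is decided from it cannot be traced, because SAP section 3 is blacked out.

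**Working it through.** **Inputs from the documents.** "In total 58 subjects are going to be randomized to the study in a 1:1 randomization" (Protocol 11.7), so 29 per arm. SD 250 mL and target difference 160 mL (Protocol 11.7). One-sided 10% (SAP 6.1.3), critical value z = 1.2816. Four post-baseline efficacy visits, at Weeks 13, 25, 37 and 49 (Protocol 3.1).

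**Assumed, because the documents are silent.** SDs at the first three of these visits. I fix the last at 250 mL and let the SD rise linearly from a first-visit value.

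**1. The plan's own figure.** Planned SE at Week 48 = 250 × √(2/29) = 65.7 mL. Power = Φ(160/65.7 − 1.2816) = 87.6% (87.2% with the noncentral t). The protocol's claim of at least 80% holds.

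**2. What AR(1) does to the SE.** To a good approximation the fitted common variance is the mean of the visit variances, so

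r = SE ratio = √(mean visit variance / Week 48 variance)

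Actual one-sided error = 1 − Φ(1.2816 × r). Coverage of the 80% interval = 1 − 2 × that error.

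For a first-visit SD of 125 mL, the SDs are 125, 166.7, 208.3 and 250. The variances are 15,625, 27,778, 43,403 and 62,500, with mean 37,326. So r = √(37,326/62,500) = 0.773, and the error is 1 − Φ(0.990) = 16.1%.

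| First-visit SD (mL) | Mean variance / Week 48 variance | r | Model SE (true 65.7 mL) | One-sided error | 80% CI coverage |
|---|---|---|---|---|---|
| 250 (constant) | 1.000 | 1.000 | 65.7 | 10.0% | 80% |
| 200 | 0.816 | 0.903 | 59.3 | 12.4% | 75% |
| 180 | 0.750 | 0.866 | 56.9 | 13.4% | 73% |
| 150 | 0.662 | 0.814 | 53.4 | 14.9% | 70% |
| 125 | 0.597 | 0.773 | 50.7 | 16.1% | 68% |

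A full large-sample AR(1) fit gives almost the same: 12.3%, 14.7% and 15.9% for 200, 150 and 125 mL. Under steeper growth (random patient slopes plus visit error of SD 50 mL, first-visit SD about 79 mL) it gives 17.6%.

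**3. Check by simulation.** REML fits of the SAP mean model under AR(1), 29 per arm, four visits, 2,500 trials per setting (Monte Carlo SE about 0.7 points), 0% and 20% dropout completely at random:

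| True pattern | One-sided error, 0% dropout | 20% dropout |
|---|---|---|
| Constant variance | 10.1% | 8.4–9.4% |
| SD 200 → 250 | 11.8% | 13.1% |
| SD 150 → 250 | 15.1% | 14.6% |
| SD 125 → 250 | 15.4% | 16.7% |
| Random slopes, error SD 50 | 16.7% | 18.7% |

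A Week 48-only ANCOVA on the same data stayed between 8.9% and 10.8% throughout. The excess therefore comes from pooling variance over visits.

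**4. Does a heterogeneous structure cure it?** In one simulation with 15% dropout (800 trials per setting, Monte Carlo error about 1 point), ARH(1) gave an error of 9–10% and coverage of 80–82%, including when variance was constant. A smaller one (500 trials per setting, about 1.5 points) gave about 12% and 77–79%. Heterogeneous Toeplitz was not simulated.

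**5. How likely is the trigger?** With four visits an unstructured matrix has 4 × 5/2 = 10 parameters for 58 patients, which should normally converge (a judgement, not a calculation). SAP Appendix 2 lists visits every four weeks from Week 5 to Week 49; twelve visits would need 12 × 13/2 = 78 parameters. The protocol's schedule has four.

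**The case against.** The strongest reply is that this will probably never matter. Unstructured is the main model, AR(1) is only permitted on non-convergence, and four visits make that remote for FVC. The study is described as exploratory and non-confirmatory. All of this stands, and it is why the point is minor.

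The driving input is also not in the documents. That stands too: with constant variance the level stays at about 10%, and with falling variance the SE would be too large.

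A reader might infer that a wrong SE would pass unnoticed. The SAP does not support that. Section 6.1.2 plans by-visit summaries of FVC change, section 4.2 includes the SD among the default statistics, and section 6.1.3.1 plans residual checks. The missing-data sensitivity analysis in Appendix 2 uses a Week 49-only ANCOVA that does not pool over visits. What remains is that none of these has a stated consequence for the choice of covariance.

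Protocol 11.7 also refers to an effect of at least 110 mL. If that means an observed estimate of at least 110 mL, it is stricter than the significance bound of 1.2816 × 65.7 = 84 mL. Its null probability is 1 − Φ(110/65.7) = 4.7%, and an understated SE would not loosen it. That protects a joint FVC decision, but not the reported test and interval. No such threshold is visible for the secondary endpoints.

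For those endpoints no variance pattern or convergence rate is available, so the shared model shows further opportunities for the fallback to be used, not a measured inflation. Any effect at an interim analysis cannot be judged, because that text is blacked out.

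**Conclusion.** The point holds conditionally. If the unstructured model fails to converge, AR(1) is adopted, and the variance of change rises towards Week 48, the Week 48 SE is understated. With an SD of 250 mL at Week 48 and 200 down to 125 mL at the first visit, the one-sided error is roughly 12–16% instead of 10%, and the 80% interval covers about 75% down to 68%. It reaches about 18% under random slopes with little visit error, and stays at 10% if variance is constant. The earlier-visit SDs are assumptions.

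A reader might infer that the trial's error rate is 16–18%. The documents do not support this: it needs a first-visit SD of roughly 80–125 mL against 250 mL, and it would apply only where the fallback is used. The main analysis as planned is unaffected. This is worth changing because it is cheap, and its severity is low.

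**What to change.** In SAP section 6.1.3, replace the AR(1) sentence with a fixed sequence that keeps a separate variance at each visit. For example: if the unstructured model does not converge, fit heterogeneous Toeplitz, then ARH(1), and use the first that converges, with Kenward-Roger degrees of freedom. State that the same sequence applies to the models in section 6.2.3.2, and make it mandatory rather than optional.

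The cost is one sentence and a changed TYPE= option in PROC MIXED. With four visits AR(1) has 2 covariance parameters, ARH(1) has 5 (four variances, one correlation) and heterogeneous Toeplitz has 7 (four variances, three correlations), so the change adds three to five. The SAP already uses ddfm=kr in Appendix 2. The particular order is a reasonable choice rather than the only one; what matters is that it is set in advance and keeps visit-specific variances.
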